8. STUDY DRUG MANAGEMENT

8.1. Description of ABI-009

8.1.1. ABI-009 Packaging, Labeling, and Storage

ABI-009 will be supplied by the Sponsor in single-use vials as lyophilized product. Each single-use 50-mL vial will contain 100 mg rapamycin and approximately 800 mg of human albumin as a stabilizer. Each vial will be labeled according to country-specific regulatory requirements for labeling of IPs.

Unopened vials of ABI-009 should be stored in a refrigerator (2°-8°C; 36°-46°F) in original cartons to protect from light. Reconstituted ABI-009 may be stored for up to 4 hours at 2-8°C (36°- 46°F), followed by 4 hours at room temperature (<25°C) in the IV bag. Both unopened vials of ABI-009 and reconstituted ABI-009 should be stored in an area free of environmental extremes and must be accessible only to study personnel.

Temperature records for ABI-009 must be made available to AADI or Sponsor nominated Contract Research Organization monitoring teams for verification of proper study drug storage.

8.2. ABI-009 Accountability, Disposal, and Compliance

Only completely unused study drug vials should be retained by the site until a representative from AADI or Sponsor-nominated CRO has completed an inventory. Partially used and completely used vials should be destroyed according to the site's guidelines, and their disposition should be recorded on the Investigational Drug Accountability Record Form.

The Investigator, or designee, shall record the dispensing of study drug to patients and any remaining study drug after dosing in a study drug accountability record. The study drug record will be made available to AADI or authorized AADI-designated monitoring personnel for the purpose of accounting for the study drug supply. Inspections of the study drug supply for inventory purposes and assurance of proper storage will be conducted as necessary. Any significant discrepancy will be recorded and reported to AADI or their designee and a plan for resolution will be documented.

Accurate recording of all ABI-009 administration will be made in the appropriate section of the patient's eCRF and source documents. The investigator or designee is responsible for accounting for all study-specific IP either administered or in their custody during the course of the study.

8.3. ABI-009 Reconstitution

NOTE: It is not a requirement to use filter needles in the preparation, or in-line filters during the administration of ABI-009. In any event, filters of pore size less than 15 microns (15 µm) must not be used.

ABI-009 will be reconstituted by appropriate study personnel and administered to the patient in the study site (see below). The Investigator will calculate the BSA of the patient in order to determine the total amount of ABI-009 to be administered.

Reconstitution and Use of ABI-009:

1. Calculate the patient's BSA according to standard institutional methods. BSA will be calculated at baseline and recalculated if the weight changes by >10%.

Calculate the total dose (in mg) to be administered by:

$$\text{Total Dose (mg)} = \text{BSA} \times (\text{study dose mg/m}^2)$$

2. Calculate the total number of vials required by:

$$\text{Total Number of Vials} = \frac{\text{Total dose (mg)}}{100 \text{ (mg/vial)}}$$

Round up the number of vials to be reconstituted to the next higher whole number when a fractional number of vials is obtained by the above formula (e.g., if the total number of vials = 4.05 or 4.5, then 5 vials would be reconstituted).

3. Using sterile technique, prepare the vials for reconstitution.
4. Swab the rubber stoppers with alcohol.
5. Reconstitute each ABI-009 vial by using a 50-cc or 60-cc sterile syringe to inject 20 mL of 0.9% Sodium Chloride Injection into each vial over a period of not less than 1 minute (Note: Change the syringes after reconstituting every 3 vials).
 - Aseptically, reconstitute each vial by injecting 20 mL of 0.9% Sodium Chloride Injection.
 - **Slowly** inject the 20 mL of 0.9% Sodium Chloride Injection over a minimum of 1 minute, using the sterile syringe to direct the solution flow onto the **INSIDE WALL OF THE VIAL**.
 - **DO NOT INJECT** the 0.9% Sodium Chloride Injection directly onto the lyophilized cake as this will result in foaming.
 - Once the injection is complete, allow the vial to sit for a **minimum of 5 minutes** to ensure proper wetting of the lyophilized cake/powder.
 - **Gently** swirl and/or invert the vial **slowly** for at least **2 minutes** until complete dissolution of any cake/powder occurs. **Avoid** generation of foam.
 - If foaming or clumping occurs, stand solution for at least 15 minutes until foam subsides.
 - Each mL of reconstituted product will contain 5 mg of rapamycin.
6. Calculate the exact total dosing volume (to the nearest mL) of 5 mg/mL suspension required for the patient:

$$\text{Dosing volume (mL)} = \frac{\text{Total dose (mg)}}{5 \text{ (mg/mL)}}$$

7. The reconstituted sample should be translucent and homogeneous without visible particulates. If unsuspended powder is visible, the vial should be **gently** inverted again to ensure complete resuspension, prior to use.
8. Using a new, sterile 50-cc or 60-cc syringe, withdraw the reconstituted ABI-009 solution. Do not remove the rubber stopper from the ABI-009 vials as this can compromise the sterility of the drug preparation.
9. Inject the calculated dosing volume of reconstituted ABI-009 suspension into an empty sterile, standard PVC or non-PVC IV bag using an injection port. Inject perpendicularly into the center of the injection port to avoid dislodging plastic material into the IV bag. Repeat steps 9 and 10 until the patient's entire required dose is injected into the IV bag.
10. Remove the injection port.
11. Once the exact volume of reconstituted ABI-009 has been withdrawn from the vials, discard any excess solution left over in accordance with standard operating procedures for cytotoxic drugs.
12. Administer the calculated dosing volume of reconstituted ABI-009 suspension by IV infusion over 30 minutes (+/- 10 min). The use of in-line filters is not necessary; if used, in-line filters with pore sizes of < 15 microns (15 μ m) should not be used. Upon completion of infusion, the infusion catheter should be flushed with ~2 mL normal saline to ensure all drug has been infused.
13. Reconstituted ABI-009 suspension in IV bag should be used immediately, but may be stored for up to 4 hours at 2-8°C (36°- 46°F), followed by 4 hours at room temperature (<25°C).

8.4. Receipt and Return of ABI-009

Upon receipt of the study drug supplies, the Investigator or designee will conduct an inventory and sign both copies of the study drug receipt and forward one copy to the address indicated on the form. One copy of the receipt and the packing slip must be retained in the Investigator's regulatory file records.

A representative from AADI or his/her designee will inspect the study drug inventory, Drug Accountability Record form(s), and will arrange for the disposition of any remaining unused study drug. No study drug may be returned to AADI without the representative from AADI or other AADI-designated personnel first inspecting the study drug inventory and accountability documentation.

9. CONCOMITANT MEDICATIONS AND PROCEDURES

All concomitant treatments, including blood and blood products, must be reported on the eCRF. Throughout the study, investigators may prescribe any concomitant medications or treatments deemed necessary to provide adequate supportive care except for those listed in [Section 9.2](#).

Concomitant therapies are to be collected from enrollment/randomization through the EOT Visit. Therapy name including indication, dose, frequency, route, start date and stop date will be recorded on each patient's eCRF(s).

9.1. Permitted Medications and Procedures

The investigator must be informed as soon as possible about any medication taken from the time of screening until the end of the clinical phase of the study (final study visit). Any concomitant medication(s), including herbal preparations, taken during the study will be recorded in the eCRF. The minimum requirement is that drug name, dose, and the dates of administration are to be recorded. Additionally, a complete list of all prior cancer therapies will be recorded in the eCRF.

Patients should receive full supportive care during the study, including transfusions of blood and blood products, and treatment with antibiotics, anti-emetics, anti-diarrheas, and analgesics, and other care as deemed appropriate, and in accordance with their institutional guidelines. WBC growth factors may be administered at the discretion of the investigator, consistent with institutional guidelines.

Extreme precaution must be taken with contraceptives (either combined or progesterone only), as it is not known if there is the potential of inhibition/induction of enzymes that affect the metabolism of estrogens and/or progestins.

9.2. Prohibited Medications and Procedures

The use of certain medications, and illicit drugs within 5 half-lives or 28 days, whichever is shorter prior to the first dose of study drug and for the duration of the study will not be allowed. If a prohibited medication is required for single use (such as for a procedure) while study drug is held, the AADi medical monitor can approve such use.

The following medications or non-drug therapies are prohibited:

- Other anti-cancer therapy while on treatment in this study.
- Antiretroviral drugs (patients with known HIV are ineligible for study participation).
- Herbal remedies (eg, St. John's wort) unless approval is granted by the medical monitor.
- Rapamycin is metabolized primarily by CYP3A4. Drugs that are strong inhibitors or inducers of CYP3A4 may only be used under special circumstances (eg, as a single use for a procedure) while treatment with study drug is interrupted. The list may be modified based on emerging data.

- Use of any known CYP3A4 substrates with narrow therapeutic window (such as fentanyl, alfentanil, astemizole, cisapride, dihydroergotamine, pimozide, quinidine, terfanide) within the 14 days prior to receiving the first dose of ABI-009. Other medications may be allowed if there is agreement between the sponsor and investigator
- Use of strong inhibitors and inducers of CYP3A4 within the 14 days prior to receiving the first dose of ABI-009

10. STATISTICAL CONSIDERATIONS

10.1. Study Endpoints, Analysis Sets, and Covariates

10.1.1. Study Endpoints

Primary Endpoint:

- Objective Response Rate evaluated by independent review assessment

Secondary Endpoint(s):

- Duration of response
- Progression-free survival rate at 6 months
- Progression-free survival
- Overall survival
- Incidence and grade of treatment-emergent AEs

Note: Analysis of secondary efficacy endpoints DOR, PFS rate at 6 months, median PFS, and median OS will be done separately for 2 subgroups of patients: 1) those with metastatic disease; and 2) those with locally advanced disease for which surgery is not an option. Patients in the locally advanced tumor subgroup may receive surgery if there is sufficient tumor shrinkage, which could introduce a bias in the assessment of the DOR, PFS rate at 6 months, median PFS, and OS. Safety will be analyzed in both patient groups together.

Exploratory Endpoint(s):

- Investigator assessed ORR
- Pharmacokinetic/pharmacodynamic relationships for safety and/or efficacy endpoints
- ABI-009 pharmacokinetic parameters including, but not limited to, maximum observed concentration (C_{max}) of rapamycin, minimum observed concentration (C_{min}), and area under the plasma concentration-time curve (AUC)
- Presence/level of expression of several tumor biomarkers and their relationship to clinical responsiveness

10.1.2. Analysis Sets

Efficacy Analysis Set

The Efficacy Analysis Dataset includes all enrolled patients with measurable tumor per RECIST v1.1 at baseline who receive at least one dose of ABI-009, and have a confirmed diagnosis of PEComa. The primary analysis of all efficacy endpoints will be performed on the Efficacy Analysis Dataset.

Full Analysis Set (Treated Population)

The Full Analysis Set includes all enrolled patients who receive at least one dose of ABI-009. All efficacy analyses will be repeated using the Full Analysis Data Set as sensitivity analyses. Analyses of safety endpoints will be performed on the Full Analysis set.

Per-protocol Analysis Set

The Per-protocol Analysis Set includes all enrolled patients who do not have any prospectively defined protocol violation. A sensitivity analysis of the primary and secondary efficacy endpoints may be performed on the PP Analysis Set.

The relationship of the following covariates to efficacy endpoints will be explored if appropriate.

10.1.3. Covariates and Subgroups

Two groups of patients will be studied, those with metastatic disease and those with locally advanced disease for which surgery is not an option. The 2 subgroups of patients will be assessed together for the primary endpoint, ORR. However, because some of the patients in the locally advanced tumor subgroup may be clinically indicated to have surgery if there is sufficient tumor shrinkage, which would introduce a bias, the 2 groups will be analyzed separately for secondary endpoints, DOR, PFS rate at 6 months, PFS, and OS.

In addition the following covariates may be used to examine efficacy and/or safety in subgroup or covariate analyses, if sufficient number of patients are enrolled in the subgroups:

- Gender (male and female)
- Age at enrollment (<65 vs ≥65 and <75 vs ≥75 years)
- ECOG Performance Status at baseline (0 vs 1)
- Time from initial diagnosis to enrollment

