Patients will be evaluated for complete response (CR), partial response (PR), stable disease (SD), or progressive disease (PD) by CT imaging. Contrast enhanced MRI can also be used, as long as the same modality is used throughout the study. Baseline scan results can be accepted from outside institutions, but must be done within 4 weeks of starting therapy and must include (as clinically indicated), chest abdominal, and pelvic CT or MRI. The first response assessment by CT or MRI scans documenting target lesions will be done 6 weeks after first treatment and should be repeated every 6 weeks for the first year, then every 12 weeks thereafter until disease progression. If an initial observation of objective response (CR or PR) is made, a confirmation scan should be done at 6 weeks after initial observation. Scans should continue on schedule regardless of delays in ABI-009 dosing. The primary endpoint, ORR, will be determined by independent radiologist(s). The independent radiologic review will follow a separate imaging charter.

After disease progression, patients will be followed for survival every 12 weeks, or more frequently as needed, until death, withdrawal of consent, or the study closes, whichever is the earliest.

Overview of Key Safety Assessments

Safety and tolerability will be monitored through continuous reporting of treatment-emergent and treatment-related adverse events (AEs), AEs of special interest, laboratory abnormalities, and incidence of patients experiencing dose modifications, dose delay/dose not given, dose interruptions, and/or premature discontinuation of IP due to an AE. All AEs will be recorded by the investigator from the time the patient signs informed consent until 28 days after the last dose of IP. Adverse events will be graded by National Cancer Institute (NCI) Common Terminology Criteria for Adverse Events (CTCAE) v4.03.

Physical examination, vital sign, laboratory assessments (eg, serum chemistry, hematology), and ECOG performance status will be monitored. All SAEs (regardless of relationship to IP) will be followed until resolution. Laboratory analysis will be performed as per study schedule.

Statistical Considerations

Efficacy Analyses:

The primary analysis will address all study objectives and it will be conducted when all patients have had the opportunity to be treated for at least 6 months. All primary, secondary, and exploratory efficacy and safety analyses will be conducted at the time

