7.2. Dose Modification and Stopping Rules

7.2.1. Dosage Adjustments, Delays, Rules for Withholding or Restarting, Permanent Discontinuation

If, treatment cannot be administered on the planned visit date, ABI-009 may be administered +/- 2 days from the scheduled date. Prior to ABI-009 administration on Day 1 of each cycle, patients must meet the following hematological requirements:

- ANC $\geq 1.5 \times 10^9/L$
- Platelet count $\geq 100 \times 10^9/L$
- Hemoglobin $\geq 9 \text{ g/dL}$

The treatment will be on hold up to 14 days until the patient has fulfilled these criteria.

Day 1 Dose Missed

If the dose held or missed was to be given on Day 1 of the next cycle, that next cycle will not be considered to start until the day the first dose is actually administered to the patient (ie, D1-D8-Rest, X-D1-D8-Rest, etc).

Day 8 Dose Is Missed

That week becomes the week of rest. Next dose (if counts and chemistries permit) becomes Day 1 of a new cycle (ie, D1-D8-Rest, D1-X, D1-D8-Rest, etc).

The maximum delay between a missed scheduled dose and the next one (whichever dose was missed) should not be longer than 14 days. Approval from the Medical Monitor is required to restart study treatment after ≥ 21 days of interruption.

Doses will be reduced for hematologic and other toxicities. Two levels of dose modifications are permitted according to the criteria below. Dose reductions will occur

sequentially (75 mg/m² and 56 mg/m²), there should be no direct reduction by two dose levels. If a toxicity requiring dose modification occurs following the second dose reduction of ABI-009, further treatment should be discontinued. Dose adjustments are to be made according to the system showing the greatest degree of toxicity. Toxicities will be graded using the NCI CTCAE Version 4.03.

Guidelines for dose modifications and interruptions for management of common toxicities associated with the study treatment(s) are provided in this section:

- General guidelines for clinically significant toxicities related to study treatment

And

- Specific guidelines for adverse events of special interest, which are events that have been observed with higher frequency or severity.

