10.5.2. Primary Efficacy Endpoint

The primary endpoint, ORR, will be determined by independent radiologist(s). The independent radiologic review will follow a separate imaging charter.

The primary analysis will evaluate the independently assessed ORR in patients treated with ABI-009 by providing the number and proportion of patients achieving OR along with an exact binomial 95% CI for the proportion.

Overall response rate is defined as the proportion of patients who achieve a confirmed PR or CR per RECIST 1.1. Patients without a post-baseline disease assessment will be considered not to have achieved a response. If an initial observation of objective response (CR or PR) is made, a confirmation scan should be done at 6 weeks after initial observation.

The analysis of ORR will be conducted on the Efficacy Analysis Dataset. A sensitivity analysis will also be conducted using the Full Analysis Dataset. Analysis of ORR will include both subgroups of patients: 1) those with metastatic disease and 2) those with unresectable locally advanced disease or resectable with multiple resections.

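### Does pooling the two disease subgroups for ORR leave the primary result exposed to surgery after tumour shrinkage?

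*Combined protocol and SAP*

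**What the plan says.** Section 10.1.3 (Covariates and Subgroups) states the pooling: "The 2 subgroups of patients will be assessed together for the primary endpoint, ORR". It gives the reason for treating the other endpoints differently: some locally advanced patients may go to surgery if the tumour shrinks enough, "which would introduce a bias, the 2 groups will be analyzed separately for secondary endpoints, DOR, PFS rate at 6 months, PFS, and OS". The optional covariates listed there are gender, age, ECOG status and time from diagnosis; disease extent is not among them.

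Section 10.5.2 (Primary Efficacy Endpoint) sets the scoring: "Overall response rate is defined as the proportion of patients who achieve a confirmed PR or CR per RECIST 1.1". It has one rule for missing assessments: "Patients without a post-baseline disease assessment will be considered not to have achieved a response". It asks for a confirmation scan six weeks after the first response, and on reading the scans it says: "The independent radiologic review will follow a separate imaging charter". It describes the second subgroup as "those with unresectable locally advanced disease or resectable with multiple resections", whereas Sections 10.1.1, 10.1.3 and 10.5.3 say surgery is not an option and inclusion criterion 1 says it is not recommended.

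Other provisions also bear on the point:

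- **Synopsis, Overview of Key Efficacy Assessments:** "Scans should continue on schedule regardless of delays in ABI-009 dosing".
- **Section 7.2.1:** the delay after a missed dose should not exceed 14 days. The same section also says "Approval from the Medical Monitor is required to restart study treatment after" an interruption of 21 days or more.
- **Section 9.2:** other anti-cancer therapy, drug or non-drug, is prohibited while on treatment.
- **Section 10.1.2:** efficacy analyses are repeated on the Full Analysis Set, and a per-protocol sensitivity analysis of the primary endpoint may be done.
- **Section 10.5.3:** DOR, PFS and OS of locally advanced patients are given as case reports.

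**The concern.** The plan names a source of bias, applies its remedy to four secondary endpoints and leaves the primary endpoint without it. ORR and its exact interval are the main result of a 30-patient single-arm trial, so one patient is worth 3.3 points.

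The exposed step is confirmation. With Cycle 1 Day 1 as day 1, scans fall on about days 43, 85 and 127. A response first read on day 43 is confirmed on day 85, so an operation between days 44 and 84 makes the confirming scan post-operative. One target lesion is enough for entry (inclusion criterion 3), so resection may leave no target lesion to measure. If such a scan were accepted, the surgeon's work could be credited to the drug. The Full Analysis Set contains every patient in the primary set, so that sensitivity analysis would not show the effect. The investigator-assessed ORR is not stated to follow the charter.

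**Working it through.** **1. The plan's own figures.** Exact (Clopper-Pearson) 95% limits with n = 30: 9/30 gives 14.7% to 49.4%. The largest half-width over all possible counts is 18.7 points, at 15/30. Both match Section 10.2.

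**2. How many patients could be involved.** Section 1.3.1 puts locally advanced disease at 10% to 15%.

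- Expected number: 30 × 0.10 = 3 to 30 × 0.15 = 4.5.
- Chance of enrolling at least one: 1 − 0.90^30 = 0.958 to 1 − 0.85^30 = 0.992.

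The subgroup will almost certainly be present, but small.

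**3. Responders resected before confirmation.** Let w be the locally advanced share, 0.30 the ORR (the plan's planning value, assumed here to hold in this subgroup) and f the share of those responders resected before the confirming scan. The documents do not give f, so it is an assumption shown over a range. The expected number is 30 × w × 0.30 × f, and the chance of at least one is 1 − (1 − 0.30wf)^30.

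| f | Expected number (w = 0.10 to 0.15) | Chance of at least one |
|---|---|---|
| 0.05 | 0.045 to 0.068 | 4% to 7% |
| 0.10 | 0.09 to 0.135 | 9% to 13% |
| 0.25 | 0.225 to 0.338 | 20% to 29% |
| 0.50 | 0.45 to 0.675 | 36% to 49% |

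The expected number stays below one throughout. These patients had already responded before surgery, so accepting a post-operative confirmation would not create a response out of nothing. The table does not cover a patient with no response before surgery who is scored only on later scans. The documents give no basis for a probability of that.

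**4. Effect of a reclassification on the estimate, starting from 9/30.**

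- One added: 10/30 = 33.3% (17.3 to 52.8).
- One removed: 8/30 = 26.7% (12.3 to 45.9).
- Three added, an extreme in which three locally advanced patients are all scored only on post-operative scans: 12/30 = 40.0% (22.7 to 59.4).

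**5. What a split ORR would show.** A metastatic row might read 8/27 = 29.6% (13.8 to 50.2) or 8/26 = 30.8% (14.3 to 51.8), against 9/30 = 30.0% (14.7 to 49.4) pooled. A locally advanced row might read 1/3 = 33.3% (0.8 to 90.6). Any gap between pooled and metastatic ORR equals w × (locally advanced rate − metastatic rate). With assumed rates of 50% and 30% that is 0.10 × 20 = 2.0 to 0.15 × 20 = 3.0 points. This is case mix and does not measure bias from surgery.

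**6. Whether the plan would score a post-operative scan as response.** Section 10.5.2 requires a confirmed PR or CR under RECIST 1.1, and Section 6.2.3 ties image evaluation to the same criteria. Whether a lesion removed by surgery can be read as a response is decided by those criteria and the charter. Section 10.5.2 gives no contrary instruction. Staying on drug after a resection would also have to be squared with the prohibition in Section 9.2 and the 14-day limit in Section 7.2.1.

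**The case for a change.** The best argument for a change is that it is cheap and that timing matters: a rule chosen once the scans have been seen is open to the charge of being data-driven. The documents repeatedly foresee surgery, and Section 1.3.1 cites a published case. Nowhere do they say that a resected patient leaves the study. The Synopsis, Section 6.2.3 and the imaging footnote to Table 2 run scans until progression, while Section 6.4 and the follow-up column of Table 2 list no imaging, so post-operative scans may exist even after drug is stopped. The per-protocol analysis is optional, and surgery is not named as a violation. The case reports do not promise surgery dates.

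Much of this stands. Section 10.5.2 is silent, the charter is not available to settle the matter, and its stated scope is the independent review. But silence is different from a rule that gives a wrong answer. An unconfirmed response is already a non-response under Section 10.5.2, and the independent readers apply RECIST 1.1 under a charter. The part outside the charter's stated scope is the investigator ORR, which is exploratory. Surgery during treatment can be traced, because Table 2 records concurrent procedures until 28 days after the last dose. Since only responders enter DOR, each locally advanced responder will appear in the case reports.

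**Conclusion.** No change follows. Pooling ORR while separating DOR, PFS and OS is coherent: surgery is conditional on shrinkage, so it tends to follow the response and to disturb what is measured afterwards. Section 1.3.1 gives response rate as the reason for enrolling both groups. The missing sentence on post-resection scans is a detail that the response criteria and the imaging charter can be expected to supply. A metastatic-only ORR would be a reasonable extra, but at 8/27 against 9/30 it adds little to a plan that Section 10.5.1 calls descriptive. The differing descriptions of the locally advanced group are a drafting inconsistency; they do not alter who is counted in the pooled ORR.

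The likely reach is no patient or one, and one patient is 3.3 points inside an interval about 35 points wide (49.4 − 14.7 = 34.7). This rests on the 10% to 15% locally advanced share, the 30% ORR, and the assumption that the charter handles resected lesions under RECIST 1.1. If the charter proved silent, the question would need settling there before the reads.
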